### Study Procedures

For Aim 1, we will maintain a master tracking file that indicates mode of invitation (handouts or flyers, word of mouth), screening and determination of eligibility, random assignment to *SMC* or waitlist control, receipt of informed consent, mode of delivery (in-person or by telehealth), and completion of assessments and intervention sessions. We will also track *SMC* uptake for waitlist controls, who will be invited to begin the *SMC* 6 weeks following baseline and immediately following the post-intervention assessment. We will enroll 3-4 participants per week (divided between intervention and control groups) during the active recruitment period.

For Aim 2, our procedures include baseline assessment for all participants, randomization to *SMC* or the waitlist control group, provision of a minimum of 4 *SMC* sessions for those in the *SMC* intervention arm, and post-intervention assessments (for both *SMC* and waitlist control groups).

For Aim 3, we will assess the acceptability of the *SMC* through post-intervention assessment feedback and through evaluation of lost-to-follow-up rates.

For Aim 4, we will examine how changes in the theorized targeted mechanisms mediate the relationship between the intervention and PTSD symptomatology, using the same assessment data utilized for Aim 2.

**Recruitment Strategy.** We will disseminate study information to all BPPN clients through informational handouts and fliers. Those interested will be invited to contact the licensed master social worker (LMSW) for screening. Women who meet all inclusion criteria and no exclusion criteria will be provided with a detailed explanation of the study, and will be encouraged to ask questions prior to providing written consent. They will then be invited to complete the baseline assessment with the LMSW. Once baseline assessment is completed, participants will be: 1) randomized to the *SMC* or waitlist control arm in a 1:1 fashion using a block randomization scheme, 2) will be mailed the *SMC* materials and 3) be assigned to the community health

worker (CHW) who will contact the participant and arrange the first session, either in-person or remotely according to the participant's preference. Consent forms will outline remuneration for each aspect of the study (\$30 for the baseline and \$40 for the post-intervention assessments).

**Structure of SMC.** Weekly client modules with embedded worksheets will facilitate and guide practice of skills specific to addressing PTSD in the perinatal period. Weekly intervention sessions will center on reinforcement of information introduced in each SMC module, emotional support, and referrals to additional services or specialists as needed. A key activity of each session is to practice applying knowledge and skills using the module's vignettes. Process guides prompt inquiry about *in vivo* management of PTSD reactions, and emotional and interpersonal reactions to events since the last session. Based on previous work, we anticipate each module will require 45 minutes of self-study prior to each session and 45 minutes of in-session time spent with the interventionist. This weekly commitment was highly acceptable in prior pilot efforts.

**Intervention Team.** We will hire and train a half-time LMSW to facilitate consent processes, complete baseline and post-intervention assessments, bill for services and provide regular clinical supervision, and will hire a full-time CHW to deliver the SMC. Both the LMSW and CHW will have experience working in perinatal health and will undergo 40 hours of training with PI [name] on the SMC. Supervised training will include review of the module content, role-playing of sessions, and fidelity to the SMC manual.

**Intervention Integrity and Safety.** A detailed treatment manual for the SMC will guide the content and flow of the sessions, and we will regularly assess for fidelity. At the end of each session, we will employ brief 'mirror image' fidelity checklists which will be completed separately by the CHW and participant. In preliminary studies these forms reached an inter-rater agreement of >94%. Co-PI [name] will review these weekly for inter-rater agreement and intervene if necessary. The sessions include monitoring of suicidality, substance use, and domestic violence. In instances where a participant expresses these concerns, the CHW and/or licensed social worker will notify the Co-PIs, who will initiate referral protocols to psychiatric, substance abuse, or domestic violence urgent care, as appropriate. The team will review each case in light of adverse event definitions and report any adverse events to the UB IRB.

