## BACKGROUND/RATIONALE

Posttraumatic stress disorder (PTSD) related to maltreatment is a strong predictor of intergenerational cycles of abuse and vulnerability. These cycles intersect during the childbearing years when unresolved trauma often adversely affects a woman's mental health. Women of color are especially at risk for developing PTSD as well as experiencing disparities related to maternal and infant morbidity and mortality. Pregnancy is an opportune time to intervene to disrupt these cycles, however, screening and treating PTSD in the perinatal period is rarely undertaken. Therefore, readily available interventions for low-resourced and high-risk settings are warranted. Our agency, Buffalo Prenatal Perinatal Network (BPPN) provides home visiting and other supportive services to pregnant women and their families who bear considerable burden of poverty, adversity, and disparities. As such, we are well positioned to conduct research to address perinatal PTSD. Our previous research has established initial acceptability and feasibility for a novel front-line PTSD-specific perinatal intervention, the *Survivor Moms' Companion (SMC)*. In the proposed study, we will advance this trajectory of research and build our capacity for mental health service provision by conducting an initial randomized controlled pilot study.

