## RESEARCH ACTIVITIES

### Study Overview

To achieve these aims, we will conduct a pilot randomized controlled trial. For Aim 1, we will assess feasibility of the *SMC* intervention through tracking and close monitoring of participant engagement, accrual, and retention rates. For Aim 2, we will conduct baseline assessments for all participants for trauma, PTSD diagnosis and symptoms, affect regulation including depression, anger expression, dissociation, and emotion regulation, as well as interpersonal sensitivity. We will then randomize participants to either the *SMC* intervention group or to the waitlist control group. Those in the *SMC* intervention ( $n = 30$ ) will receive a minimum of 4 *SMC* modules and corresponding weekly sessions with an interventionist prior to completing the post-intervention assessment. Those in the waitlist control ( $n = 30$ ) will complete a post-intervention assessment at 6 weeks following their baseline assessment and will then be offered the *SMC* intervention. We will use intent-to-treat analyses to evaluate the preliminary efficacy of the *SMC* for reducing PTSD. For Aim 3, we will examine post-intervention indices of client satisfaction and evaluation of drop-out rates. For Aim 4, we will examine how changes in the theorized targeted mechanisms mediate the relationship between the *SMC* intervention and PTSD. We will utilize knowledge gained to prepare applications for continued evaluation of the impact and implementation of *SMC*. Prior to beginning any study activities, we will apply for approval with the Institutional Review Board (IRB) at the University at Buffalo and will require human subjects training for all study team members through the Collaborative Institutional Training Initiative (CITI Program).

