### Participants

**Recruitment Site and Sample Size.** We will recruit pregnant participants at BPPN, which provides services to over 800 families per year; services begin in pregnancy and include screening for risk factors and stressors and supportive home-based services. Consistent with the NIH-wide initiative to increase diversity in research, recruiting at BPPN ensures representation of women of color. Based on the previous *SMC* pilot studies, we expect that 30% who initially consent to the study will not complete the full 4 intervention sessions. We plan to enroll and randomize 78 participants to retain 60 (30 *SMC*, 30 waitlist control).

**Eligibility Criteria.** Inclusion criteria are: (1) English-speaking, (2) currently pregnant and after 12 weeks but before 30 weeks gestation to allow for study completion prior to expected delivery, (3) aged 18 and older, (4) a history of trauma and PTSD, (5) able to comprehend the study protocol, consent form and provide written consent, and (6) able to commit to a minimum of 4 weekly intervention sessions. Exclusion criteria are: (1) non-English-speaking, (2) less than 18 years of age, (3) those with psychotic conditions or developmental disabilities requiring guardianship, (4) those with high-risk pregnancies necessitating extended bedrest or inpatient care, and (5) those unable to commit to completing the intervention sessions.

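### Explicit monitoring of suicidality, substance use and domestic violence is described only inside SMC sessions; elsewhere the plan offers a PHQ-9 at baseline and post-assessment with no stated response rule

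*Combined protocol and SAP*

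**What the plan says.** **Monitoring.** Under Intervention Integrity and Safety: "The sessions include monitoring of suicidality, substance use, and domestic violence". The route that follows is not limited to one arm: "In instances where a participant expresses these concerns, the CHW and/or licensed social worker will notify the Co-PIs", after which the Co-PIs start referral. Cases are then reviewed against adverse event definitions, and adverse events are reported to the IRB.

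**Waitlist timing.** Under Study Overview, waitlist women "will complete a post-intervention assessment at 6 weeks following their baseline assessment". Under Study Procedures, they are invited to begin the SMC "6 weeks following baseline and immediately following the post-intervention assessment". They therefore have no sessions during the wait.

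**Assessments in both arms.** Recruitment Strategy says of eligible women who have consented: "They will then be invited to complete the baseline assessment with the LMSW". The Intervention Team paragraph has the same social worker complete the post-intervention assessments. Measures schedules a post-assessment for everyone randomized, including women who do not complete. Table 2 places the PHQ-9 at both time points, under the theorized mechanisms of change. Measures limits the in-session distress rating to the SMC arm.

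**Other contacts.** Background/Rationale says the agency "provides home visiting and other supportive services to pregnant women and their families", and Participants adds that "services begin in pregnancy and include screening for risk factors and stressors and supportive home-based services". Risks/Blockers and Mitigation Strategies plans regular contact with all participants to keep them engaged.

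**Expected non-completion.** Under Participants, "we expect that 30% who initially consent to the study will not complete the full 4 intervention sessions".

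**The concern.** Everyone enrolled is pregnant and has a history of trauma and PTSD. The sponsor judged suicidality, substance use and domestic violence important enough to monitor in the intervention sessions. Sessions work on traumatic reactions, so monitoring there makes sense. But the three risks do not arise only from the intervention, and they do not stop when a woman is allocated to wait or stops attending.

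The referral route begins when a participant expresses a concern. In sessions, someone is stated to be monitoring. Outside sessions, no safety questions are stated for the study assessments or the retention contacts. Detection then depends on the woman raising the matter, on agency services that are not study procedures, or on someone acting on a PHQ-9 that the plan treats as a research measure. What is at stake is the timely recognition of a concern, not the validity of the efficacy comparison.

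**Working it through.** The plan states no figure on this point to reproduce. The check reads the text and Table 2 by arm and time point, then sizes the groups.

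**1. What is scheduled, and when**

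| Period | Waitlist arm | SMC arm |
|---|---|---|
| Baseline | PHQ-9 with the social worker | PHQ-9 with the social worker |
| Between assessments, attending | Not applicable | Monitoring of the three risks in sessions, plus distress rating |
| Between assessments, not in sessions | No study safety enquiry stated | No study safety enquiry stated |
| Post-assessment | PHQ-9 at week 6 | PHQ-9, including for women who stopped attending |

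**2. Table 2 by entry.** There are 3 eligibility + 3 adversity/PTSD + 4 mechanism + 4 attendance, satisfaction and distress entries, 14 in all. None is named as a measure of current substance use or domestic violence. The content of the background questionnaire is not given, and it is an eligibility form only. The PHQ-9 is the only related entry scheduled outside sessions. The documents do not print its items; that it includes a self-harm item is an assumption. No text says that anyone reads it for risk at the visit.

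**3. Women affected.** Inputs from Participants and Recruitment Strategy: 78 randomized 1:1, 60 to be retained, 30% not completing four sessions.

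- Waitlist: 78 / 2 = 39.
- SMC women stopping early, at 30%: 0.30 × 39 = 11.7, about 12.
- SMC women stopping early, at the loss implied by 78 falling to 60: 1 − 60/78 = 23%, and 39 × 0.23 = 9.
- Total spending part of the study outside session monitoring: 39 + 9 = 48 to 39 + 12 = 51 of 78, or 62% to 65%.

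**4. Time to the next scheduled assessment.** For a waitlist woman this is 6 weeks from baseline. For the SMC arm, assume weekly sessions with session k in week k, and a post-assessment at week 5 to 6 (from the 5-week column in Table 2 and the 6-week wait).

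- Stops after 0 sessions: 5 to 6 weeks from baseline.
- Stops after 3 sessions: 5 − 3 = 2 to 6 − 3 = 3 weeks.
- Completes 4 sessions, for comparison: 5 − 4 = 1 to 6 − 4 = 2 weeks.

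These intervals end at a PHQ-9. For substance use and domestic violence, no stated study question ends them.

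**The case against.** The strongest reply is that the plan is not silent outside sessions. Every woman has a PHQ-9 with the social worker before randomization, and every randomized woman is scheduled for a second. That social worker is named in the referral route, which covers any participant. The agency screens for risk and visits homes, and regular contact is planned for all. The treatment manual, referral protocols and adverse event definitions are not in the supplied text and may fill the gap.

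Much of this stands. A reader might infer that waitlist women have no scheduled enquiry bearing on suicidality at any time. The documents do not support that: if the PHQ-9 has its usual self-harm item, suicidality is asked about at baseline and post-assessment in both arms, and what is missing is a response rule. Nor do they support an inference that women are left unprotected or that events would be missed. The gap shown is one of description.

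The reply does not cover everything. No substance-use or domestic-violence measure is named outside sessions. Nothing on safety is stated for the study between a waitlist woman's two assessments. Agency services are not tied to study notification or adverse event review. The retention contacts have a stated purpose of encouraging participation, with no safety content and no timing, staff or mode.

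**Conclusion.** The point holds and should be acted on, with medium confidence because the referral protocols and adverse event definitions could not be read. Explicit monitoring of the three risks is described only in SMC sessions. As written, about 39 waitlist women have no stated study safety enquiry between baseline and week 6. About 9 to 12 SMC women have none from when they stop attending until their post-assessment. At those assessments the PHQ-9 is present but carries no review or referral rule, and substance use and domestic violence have no named measure.

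The group sizes rest on 1:1 allocation of 78 and on the plan's own non-completion figures. They count women outside session monitoring, not risk or harm, which the documents do not allow to be estimated. A reader might also infer that the efficacy result is compromised. It is not: the PCL-5 is measured at the same two assessments in both arms whatever is done here.

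**What to change.** 1. At the existing baseline and post-intervention assessments in both arms, have the social worker ask the same brief questions on suicidality, substance use and domestic violence. Ask in private; if the contact is remote, confirm first that the woman is alone, and otherwise rearrange.
2. Have the social worker review the PHQ-9 the same day, and act on a suicidality response or a score above a stated cut-off.
3. Send any concern through the existing notification, referral and adverse event review. This needs one linking sentence, since the route already covers both arms.
4. When a retention contact takes place during the wait or after a woman stops attending, add the same questions. The social worker should preferably ask them, to keep the SMC interventionist apart from untreated controls. No new dated visit is required, and the plan fixes no mid-wait contact that could be relied on as one.

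In-session monitoring stays as it is. If the referral protocols already schedule these checks in both arms, cross-reference them instead.

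**Cost.** Protocol wording, one short form, brief training and IRB review, with no new staff or visits. For the two assessments, contacts number 78 + 60 = 138 to 78 × 2 = 156. The durations and positive rates below are assumptions.

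- Asking, 5 to 10 minutes each: 138 × 5 = 690 min (11.5 h) to 156 × 10 = 1,560 min (26 h).
- Following up 10% to 30% positive answers at 30 minutes each: 138 × 0.10 × 30 = 414 min (6.9 h) to 156 × 0.30 × 30 = 1,404 min (23.4 h).
- Total: 18.4 to 49.4 h.
- Duration at 3 to 4 enrolments a week: 78/4 + 6 = 25.5 to 78/3 + 6 = 32 weeks.
- Weekly load: 18.4/32 = 0.6 h to 49.4/25.5 = 1.9 h, or about 3% to 10% of an assumed 20-hour social worker week.

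Questions at retention contacts add a few minutes each, plus follow-up of positive answers; the plan does not say how many such contacts there will be. The other downside is possible slight dilution of the arm contrast, if enquiries lead to referrals for waitlist women during the wait.

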**Table 2: Study Measures**

Measure	Eligibility	Baseline	During Intervention (5 weeks)	Post-Intervention
Eligibility				
Demographics/Background Questionnaire	X			
Childhood Trauma Questionnaire (CTQ) 	X			
Primary Care PTSD Screen for DSM-5 (PC-PTSD-5) 	X			
Adversity/PTSD Outcomes				
Adverse Childhood Experiences Questionnaire (ACE) 		X		
PTSD Checklist for DSM-5 (PCL-5) 		X		X
Dissociative Subtype of PTSD Scale (DSPS) 		X		X
Theorized Mechanisms of Change				
Patient Health Questionnaire-9 (PHQ-9) 		X		X
State Trait Anger Expression Inventory (STAXI-AX) 		X		X
Symptoms Checklist-90 Revised/Interpersonal Sensitivity Subscale (SCL-90/IPS) 		X		X
Difficulties in Emotion Regulation Scale Short Form (DERS) 		X		X
Treatment Attendance, Satisfaction, Distress				
Number of Completed Modules/Sessions			X	
Client Satisfaction Questionnaire (CSQ-8) 				X
Fidelity Checklist			X	
Subjective Units of Distress (SUD) 			X	

## Measures

We plan to use reliable and valid measures, these and their schedule of use are listed in **Table 2**. For **eligibility screening** we will use the 5 sentinel items from the Childhood Trauma Questionnaire (CTQ), and the Primary Care PTSD Screen for DSM-5 (PC-PTSD-5). For the **baseline assessment** we will assess trauma exposures, PTSD and its dissociative subtype, and measurements related to the theorized mechanisms of change, including for affect regulation and interpersonal sensitivity. All of these will be repeated at the **post-intervention assessment**. Also, at post-intervention, participants in the SMC arm will complete the

Client Satisfaction Questionnaire (CSQ-8), and invite feedback regarding perception and experience of in-person vs telehealth sessions based on their choice of modality. For those in the SMC arm we will utilize two measures during each weekly intervention session: SMC fidelity checklists, as well as Subjective Units of Distress (SUD). The SUD will be assessed on a 0-10 scale by asking the participant to rate any distress experienced ahead of session, at mid-session, and at the close of the session. Those with SUD rating of 5 or above at the session's end will be encouraged to participate in a brief relaxation exercise until their rating is reduced to 4 or lower. All who complete baselines and are randomized will be scheduled for the post-assessment; those who fail to complete will be scheduled based on their anticipated completion date.

### **Proposed Analysis**

**Data Quality Management.** Biostatistician [name] and PI [name] will oversee data collection, management, and storage using UB's established IT infrastructure. A created Data Management Plan will track any critical milestones and data review activities. A full study build will be implemented with use of REDCap and all necessary electronic case report forms (eCRFs) will be created in direct contact with relevant study personnel. Rigorous quality control procedures will be implemented so as to ensure data integrity.

**Effect Size and Power Calculations.** Because data will be generated as part of a pilot case-control study, our hypotheses should be viewed as exploratory. Analyses will be conducted to not only test the predictions, but also to examine effect sizes. If effects are clinically meaningful, effect sizes will be used to inform power calculations for a larger, planned Stage II clinical trial.

**Data Analyses.** The amount and nature of missing data for study variables will be characterized and no method of imputation will be used for missing data for primary analyses. The robustness of primary results will be assessed using several statistical techniques including multiple imputation. Outcome variables will be summarized overall and by relevant demographic and baseline variables. Descriptive statistics will be computed for all categorical variables. Numeric variables will be summarized using mean, standard deviation and range. Statistical tests will be carried out using SAS version 9.4 (or higher) statistical software (Cary, NC).

**Aim 1 Analyses.** Feasibility will be assessed via timely recruitment of participants, and through high study retention (70%). This will be carefully tracked and monitored closely by the Co-PIs.

**Aim 2 Analyses.** To describe the observed variability in the data and test for differences between groups, a linear mixed model will be fit to each considered outcome at each post-baseline measurement. Each outcome will be modeled as a function of randomized group assignment and the baseline value of the outcome variable, both treated as fixed effects. Once the model is fit, a linear contrast based on the estimated model parameters will be constructed and used to test for the overall effect of random assignment using an approximate F-test as implemented by SAS PROC MIXED. A point estimate and corresponding confidence interval to quantify group differences will be provided. Subject-level covariates predictive of outcome and their interactions with randomized assignment, such as modality (in-person vs telehealth) will be added to the models as a series of supportive analyses. To evaluate the robustness of initial analysis results, these models will be moreover used to evaluate the group effect within subgroups. Analyses will be conducted using intent-to-treat. All tests will be two-sided and tested at a 0.05 nominal significance level. Standard diagnostic plots will assess model fit and transformations of variables may be considered to meet statistical assumptions.

**Aim 3 Analyses.** We will examine acceptability of the SMC by evaluating the percentage of completion and drop-out rates as compared to similar PTSD treatments and through analysis of the CSQ scores

**Aim 4 Analyses.** We hypothesized that the effect of the intervention on PTSD symptomatology is mediated by emotion regulation and interpersonal sensitivity, that is, that there is a direct and indirect effect of the SMC on PTSD symptomatology. A generalized linear model-based approach will be utilized. After establishing the total effect of the SMC on PTSD symptomatology in the context of the unmediated model of Aim 2, the effects of the intervention on the theorized targeted mechanisms will be estimated. This will be followed by the conduct of a multiple regression analysis with each of the factors (considered one at a time) and the SMC as independent variables in the prediction of PTSD symptomatology. This approach allows for estimation of the direct and indirect effects. The 95% confidence intervals for mediated effects will be based on bias-corrected bootstrap methods, which uses the cumulative distribution functions of the bootstrap parameter estimates to determine the upper and lower endpoints of the confidence intervals. The percentages mediated of total effect of the SMC on PTSD symptomatology will be calculated. Additional analyses with interaction terms between the SMC with emotion regulation and interpersonal sensitivity will be conducted and compared.

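### The supportive Aim 2 interaction of session modality with randomised arm cannot give a valid estimate, because modality is chosen after randomisation and the waitlist arm has none when its outcome is measured; the primary contrast is unaffected

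*Combined protocol and SAP*

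**What the plan says.** The Aim 2 paragraph of Proposed Analysis sets a primary model with two fixed effects, randomised arm and the baseline value of the outcome. It then plans supportive models with further subject-level covariates: "their interactions with randomized assignment, such as modality (in-person vs telehealth) will be added to the models as a series of supportive analyses". Modality is the only covariate named. The next sentence uses the same models to look at the group effect within subgroups, and the paragraph states an intent-to-treat analysis.

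Other sections fix when modality arises:

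- Study Procedures (Recruitment Strategy) lists the steps after baseline. Randomisation is first. Contact by the community health worker is third, and the first session is then arranged "either in-person or remotely according to the participant's preference".
- Measures also treats modality as the participant's decision. Feedback in the SMC arm covers the "experience of in-person vs telehealth sessions based on their choice of modality".
- Study Overview says that waitlist participants "will complete a post-intervention assessment at 6 weeks following their baseline assessment and will then be offered the" intervention.
- Study Procedures gives the same timing: the waitlist start is "6 weeks following baseline and immediately following the post-intervention assessment".
- The tracking file in Study Procedures includes "mode of delivery (in-person or by telehealth), and completion of assessments and intervention sessions". A separate sentence tracks "uptake for waitlist controls, who will be invited to begin the" intervention.

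No section records a modality preference from both arms before randomisation.

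**The concern.** An arm-by-covariate interaction asks whether the arm effect differs between levels of a characteristic that both arms have, and that allocation cannot have influenced. Session modality fails both conditions. It belongs to the delivery of the SMC, it is settled after allocation, and in the waitlist arm it does not exist at the time of the post-test.

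Two things could go wrong. The interaction may be inestimable, and any modality coefficient that is still reported would be a self-selected contrast within the SMC arm, open to being misread as effect modification. Or waitlist modality may be supplied from a later source. The model then fits without warning, but its interaction and modality-specific arm effects have no causal reading. This matters because the plan intends to use effect sizes from the pilot to inform a Stage II trial, where a spurious modality effect could influence the choice of delivery mode.

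**Working it through.** The plan gives no figure for this analysis, so there is none to reproduce. The check has three parts.

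**1. Can the interaction be estimated?** The columns are intercept, baseline value, arm (1 = SMC), modality M and arm × M. The planned retained sample is 30 per arm; the ranks are the same at 39 per arm (78 randomised, 1:1).

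| Waitlist modality | Consequence | Rank / columns |
|---|---|---|
| Coded 0 | arm × M = M | 4 of 5 |
| Coded 1 | arm × M = M + arm − 1 | 4 of 5 |
| Missing | all controls drop out; arm is constant and arm × M = M | 3 of 5 |
| Third level 'none' | 'none' = 1 − arm; arm × 'none' = 0; arm × telehealth = telehealth | 4 of 7 |
| Filled in from later uptake | no aliasing | 5 of 5 |
| Primary model (no modality) | no aliasing | 3 of 3 |

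In the first four rows no interaction is estimable. What remains is one modality contrast within the SMC arm. With missing coding, the arm effect in that supportive model is lost as well.

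**2. What if waitlist modality were filled in from later uptake?** The value is set after the post-test, may depend on it, and is absent for women who decline. Leaving those women out also departs from the stated intent-to-treat analysis.

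A simulation illustrates the effect at 30 per arm. Its assumptions, none of them from the plan, are: outcome SD 1; baseline-outcome correlation 0.5; a true arm effect of -0.50 SD in both modalities, so no true interaction; and full uptake. The odds of choosing in-person rise by the stated ratio per SD of the score. That score is the post-test in the waitlist arm and the untreated severity (the score without the SMC effect) in the SMC arm. The fit is least squares of post-test on baseline, arm, M and arm × M.

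| Odds ratio, waitlist | Odds ratio, SMC | Mean false interaction (SD) | Rejection at 5% |
|---|---|---|---|
| 1 | 1 | 0.00 | 5% |
| 1.5 | 1 | -0.30 | 10% |
| 2 | 1 | -0.48 | 18% |
| 3 | 1 | -0.68 | 32% |
| 2 | 1.5 | -0.18 | 7% |
| 2 | 2 | about 0 | 5% |
| 3 | 3 | about 0 | 5% |

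In the row with odds ratios 2 and 1, the apparent arm effects are -0.74 SD (in-person) and -0.26 SD (telehealth): -0.74 − (-0.26) = -0.48. If choice follows the baseline score, which the model adjusts for, the bias is again about zero, even when only the waitlist arm selects. The false interaction therefore comes from outcome-related selection that differs between arms, not from selection alone.

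**3. How precise is the comparison that remains?** For modality within 30 SMC participants, ignoring baseline adjustment, the 95% half-width in SD units is t(0.975, 28) × √(1/n₁ + 1/n₂):

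- 15 vs 15: 2.048 × 0.365 = 0.75 SD
- 24 vs 6: 2.048 × 0.456 = 0.93 SD

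Both splits are assumptions.

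**The case against.** The case on the other side has four parts.

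- **Reach.** The analysis is labelled supportive, modality is introduced only as an example, and under Effect Size and Power Calculations the plan says that "our hypotheses should be viewed as exploratory". Modality is not named as a subgroup; that follows only from the sentence that reuses the same models. All of this stands, and it limits the importance of the point.
- **Filling in is conjecture.** The plan nowhere says that waitlist modality will be taken from later uptake. It tracks mode of delivery and waitlist uptake in separate sentences, and recording the mode for waitlist uptakers is an inference. This stands too. Filling in is a possibility to close off, not a stated intention.
- **A preference might exist in both arms.** Read literally, the three steps after baseline are not restricted to the SMC arm, so a preference could be noted for everyone at contact with the community health worker. Such a model could be fitted, and the value would precede the outcome. It would still be post-randomisation, given by women who may already know their allocation, so it would not be a valid moderator.
- **The size of the bias.** A reader might infer that a false interaction of -0.3 to -0.7 SD is to be expected, or that only an odds ratio of 1 avoids bias. Neither is supported. That range needs outcome-related choice in the waitlist arm alone. The bias is about zero when both arms select equally on untreated severity, or when choice follows baseline score. The documents give no basis for preferring any pattern.

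**Conclusion.** The point holds. As written, the plan names an arm-by-modality interaction that its own timing rules out. That conclusion rests only on the stated order of events and on the rank of the design matrix, and it needs no simulation assumption. The false interactions, from about zero to about -0.7 SD, are illustrations of what filling in could do. They depend on assumed odds ratios, full uptake and an assumed baseline correlation of 0.5.

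A reader might go further and infer that the main Aim 2 result is compromised, or that all planned interactions and subgroups are invalid. The documents do not support either. The primary model contains no modality term and has full rank, and interactions of arm with variables recorded before randomisation are sound in this respect. Nor does it follow that modality can never be studied as a moderator: a preference asked of everyone before randomisation would serve.

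**What to change.** In the Aim 2 analyses:

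1. Remove actual session modality as an example of a covariate to interact with arm, and do not use it as a subgroup for the arm effect.
2. Limit arm-by-covariate interactions and subgroups to variables recorded before randomisation.
3. Report actual modality only as a descriptive, non-randomised comparison within the SMC arm.
4. If moderation by modality is of interest, ask every participant for her preferred modality at baseline, before randomisation, and use that variable instead.

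Items 1 to 3 are a short change of wording, with no new data and no change to the primary model. Item 4 is optional and adds one baseline question. The downside is that the descriptive comparison will be imprecise, as the half-widths above show, and should be reported with its interval and without a claim of effect modification.
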